**1.2 Secondary Objectives:**

- To assess the PD response rate between arms (dolcanatide versus placebo).
- To confirm the safety and tolerability of dolcanatide, as compared to placebo.

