## 8.4 Off-Study Criteria

Participants may go “Off-Study” for the following reasons: development of an adverse event or serious adverse event, death, lost to follow-up, participant withdrawal, physician decision, protocol violation, complete study, or other (with detailed comments provided). Reason(s) will be noted in the participant’s research records, with the primary reason clearly identified. The participant will be classified as (Off Study/Off Agent). Data submission and follow-up after participants are determined to be “Off-Study/Off-Agent” for specific situations is noted below:

A registered participant is deemed ineligible if the participant did not satisfy each and every eligibility criterion at the time of study entry, for example, identified based on an audit or through the case evaluation process.

- If participants received study intervention, on-study materials and all data up until the point of confirmation of ineligibility will be submitted.
- If participants did not receive study intervention, on-study materials must be submitted. No further data submission is necessary. No follow-up is required.

Major Treatment Violation: A registered participant is deemed as being in major treatment violation by the coordinating center, if the participant’s very first treatment/intervention administration is so grossly administered in error, that the participant’s data can no longer be used for the primary endpoint. These cases are typically rare.

- On-study material and all data up until the point of confirmation of a major violation must be submitted.

Cancel/Participant Withdrawal: A registered participant is deemed a cancel if he/she refuses the study or withdraws consent before any study intervention is given. On-study material must be submitted. The Off Study case report form must be submitted. No follow-up is required.

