**To confirm the safety and tolerability of dolcanatide:** Summary statistics and frequency tables will be used to describe the data in an exploratory fashion. All adverse events will be summarized by treatment arm and compared between arms using the Fisher's Exact test. All eligible participants initiating study intervention will be considered evaluable for this endpoint.

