### 13.7 Evaluation of Toxicity

All registered and treated participants will be evaluable for adverse events (AEs) from the time of their first dose of dolcanatide. To evaluate the AE profile for this treatment, the maximum grade for each type of adverse event will be recorded for each participant and frequency tables will be reviewed to determine the overall patterns. The number and severity of adverse events will be tabulated and summarized across all grades. Grade 2+ adverse events will be similarly described and summarized separately. As per NCI CTC Version 4.0, toxicities are defined as adverse events that are classified as either possibly, probably, or definitely related to the interventional agent. Overall toxicity incidence, as well as toxicity profiles will be explored and summarized. Frequency distributions, graphical techniques, and other descriptive measures will form the basis of these analyses. In addition, we will review all adverse event data that are graded as 3, 4, or 5 and classified as either "unrelated or unlikely to be related" to the study intervention in the event of an actual relationship developing.

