### **13.8 Evaluation of Response**

The determination of response is described in the Section 13.4. All eligible participants having initiated study intervention and having both the pre- and post-intervention biopsies will be considered evaluable for the primary endpoint.

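### Sections 13.5 and 13.7 define the adverse-event set differently, so the between-arm comparison can leave out treated participants later found ineligible

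*Combined protocol and SAP*

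**What the plan says.** The second secondary objective in section 1.2 is comparative: "To confirm the safety and tolerability of dolcanatide, as compared to placebo". The paragraph on safety and tolerability in section 13.5 carries it out: "All adverse events will be summarized by treatment arm and compared between arms using the Fisher's Exact test". It then sets the population: "All eligible participants initiating study intervention will be considered evaluable for this endpoint".

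Section 13.7 sets a population for the same kind of data: "All registered and treated participants will be evaluable for adverse events (AEs) from the time of their first dose of dolcanatide". It has no eligibility condition.

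Section 8.4 explains how the two can part. "A registered participant is deemed ineligible if the participant did not satisfy each and every eligibility criterion at the time of study entry", and it gives an audit or case evaluation as examples of how this comes to light. For those already treated, it adds: "If participants received study intervention, on-study materials and all data up until the point of confirmation of ineligibility will be submitted".

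Section 8.3 lists ineligibility among the reasons for coming off agent. It says participants continue to be followed for safety on the planned schedule where possible, and refers to 8.4 for data submission.

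Section 13.8 uses the same eligibility condition for the primary endpoint: "All eligible participants having initiated study intervention and having both the pre- and post-intervention biopsies".

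**The concern.** A person who has taken study agent belongs in the safety comparison, whether or not an eligibility error is found afterwards. Section 13.5 as written takes that person out, while 13.7 keeps the same person in. Both sections lead to adverse-event tables, and neither they nor section 13.6, which is headed Reporting and Exclusions, says which definition prevails.

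Two things are at stake. The report could carry two adverse-event summaries with different denominators. And if the choice between them is left open until the data are seen, it could be made knowing which set gives the more favourable comparison. In arms of 12, one person is visible in the result.

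**Working it through.** **Side by side**

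| | 13.5 | 13.7 |
|---|---|---|
| Who counts | eligible and started intervention | registered and treated |
| Treated, later found ineligible | out | in |
| Output | summary by arm, Fisher's exact test | frequency tables, maximum grade, toxicity |

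Participants are randomised at registration (section 6.9), so the 13.7 set amounts to everyone randomised and treated. If k1 and k0 treated participants are later found ineligible on dolcanatide and placebo, 13.5 gives denominators of 12 − k1 and 12 − k0, and 13.7 gives up to 12 and 12. The documents give no expected k1 or k0. If both are zero, the sets are identical.

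**The plan's own figure.** The denominator of 12 comes from section 13.4: 2 × (1.645 + 0.84)² = 12.35, rounded to 12. This reproduces, and nothing here changes it.

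**Effect of one removal on a rate.** With x events among 12:
- Removing a case: x/12 − (x − 1)/11 = (12 − x)/132.
- Removing a non-case: x/11 − x/12 = x/132.

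At an assumed x = 8 (66.7%), removing a case gives 7/11 = 63.6%, a fall of 4/132 = 3.0 points. Removing a non-case gives 8/11 = 72.7%, a rise of 8/132 = 6.1 points. The maximum, 11/132 = 8.3 points, occurs only when 1/12 loses its case or 11/12 loses its non-case.

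**Effect on the Fisher test (two-sided, assumed counts)**
- 8/12 vs 2/12: p = 0.036.
- One dolcanatide case removed, 7/11 vs 2/12: p = 0.036.
- A dolcanatide case and a placebo non-case removed, 7/11 vs 2/11: p = 0.080.

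The choice of set can move a nominal result across 0.05, but need not.

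**Primary set (13.8), a separate matter.** Power of a two-sample t-test, one-sided 5%, effect size 1, is the probability that a noncentral t with n1 + n0 − 2 degrees of freedom and noncentrality 1/√(1/n1 + 1/n0) exceeds its critical value:
- 12 vs 12: noncentrality 2.449, 22 df, power 76.7%.
- 11 vs 12: noncentrality 2.396, 21 df, power 74.9%.
- 11 vs 11: noncentrality 2.345, 20 df, power 73.2%.

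One exclusion costs 76.7 − 74.9 = 1.8 points on these rounded figures. The fall to 73.2% needs one exclusion in each arm.

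**The case against.** The case against giving this much weight is good, and it rules out several stronger readings.

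- **That placebo participants have no adverse-event window.** A reader might infer this because 13.7 starts the count at the first dose of dolcanatide and the placebo capsules contain methyl cellulose (section 6.6). But that phrase is a start time. Membership is set by being registered and treated, 13.5 compares the arms, and the schedule in 7.1 records events identically for all. Blinded clinic staff could not apply an arm-specific window. It is a wording slip.
- **That safety follow-up stops once ineligibility is confirmed.** Section 8.3 says otherwise. In 8.4, the waiver of follow-up for ineligible participants covers only those not treated. What remains is narrower: 8.4 requires data only up to confirmation, so events seen later under 8.3 might not have to be submitted. If ineligibility is found after the last scheduled visit, no visit data are lost.
- **That their adverse events vanish from the safety record.** They would still be in the 13.7 tables, and the stopping rule in 13.7.1 has no eligibility condition. Only the 13.5 summary and Fisher test, which the plan calls exploratory, would omit them.
- **That the eligibility condition in 13.8 biases the primary comparison.** Eligibility rests on facts at study entry, and section 6.9 keeps the study double-blind until after specimen analysis. The documents show no route by which exclusion would depend on arm.

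It is also fair to say that treated-ineligible participants may be rare. This is a 24-person, single-site study, with eligibility checklists sent to the central registration office at both pre-registration and registration.

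None of this removes the core point. The two populations differ on their face, and 8.4 names the group for which they differ.

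**Conclusion.** The inconsistency between 13.5 and 13.7 is real and should be corrected. A stated rule would drop treated people from the comparison with placebo, while another section counts them.

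The size depends on two things the documents do not give: how many treated participants are found ineligible, and the event rates. At the assumed 8/12, one removal shifts the arm's rate by 3.0 or 6.1 points, and 8.3 points is the ceiling. With no such participant there is no effect. Sample size does not change.

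The wording of the start time and the 8.4 cut-off are minor items to tidy alongside. The primary set in 13.8 is a separate, lesser and more debatable point: one exclusion lowers t-test power at effect size 1 from 76.7% to 74.9%.

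**What to change.** 1. In 13.5 and 13.7, use one safety set: all randomised participants who took at least one dose of study agent, dolcanatide or placebo.
2. In 13.7, count events from the first dose of study agent rather than of dolcanatide.
3. Reconcile 8.4 with 8.3, so that adverse-event data from treated participants later found ineligible are submitted for as long as they are followed.
4. As a separate and optional change, let 13.8 include every randomised participant with both biopsies, and make exclusion for ineligibility a sensitivity analysis.

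The cost is protocol wording and at most a few extra follow-up forms. The change should be made before unblinding, so that the denominator is not chosen with the results in view.

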### 13.6 Reporting and Exclusions

Given the fact that participants will receive one 7-day course of treatment, we do not anticipate having any drop-outs. There will be no run-in phase for this study. It is acceptable to have a single missed dose, with the exception of Day 7 dose.

### 13.7 Evaluation of Toxicity

All registered and treated participants will be evaluable for adverse events (AEs) from the time of their first dose of dolcanatide. To evaluate the AE profile for this treatment, the maximum grade for each type of adverse event will be recorded for each participant and frequency tables will be reviewed to determine the overall patterns. The number and severity of adverse events will be tabulated and summarized across all grades. Grade 2+ adverse events will be similarly described and summarized separately. As per NCI CTC Version 4.0, toxicities are defined as adverse events that are classified as either possibly, probably, or definitely related to the interventional agent. Overall toxicity incidence, as well as toxicity profiles will be explored and summarized. Frequency distributions, graphical techniques, and other descriptive measures will form the basis of these analyses. In addition, we will review all adverse event data that are graded as 3, 4, or 5 and classified as either "unrelated or unlikely to be related" to the study intervention in the event of an actual relationship developing.

### **13.7.1 Adverse Event Stopping Rule**

The trial will be monitored closely for occurrence of adverse events by the study team and by the Mayo Clinic Cancer Center Data Safety and Monitoring Board (DSMB) using the adverse event (AE) stopping rule specified below.

**Adverse Event Stopping Rule:** The stopping rule specified below is based on the knowledge available at study development. We note that the Adverse Event Stopping Rule may be adjusted in the event of either (1) the study re-opening to accrual after any temporary suspension or (2) at any time during the conduct of the trial and in consideration of newly acquired information regarding the adverse event profile of the treatment(s) under investigation. The study team in consultation with the Mayo DSMB may also choose to suspend accrual because of unexpected adverse event profiles that have not crossed the specified rule below.

Accrual will be temporarily suspended to this study if at any time we observe events considered at least possibly related to study treatment (i.e., an adverse event with attribute specified as "possible", "probable", or "definite") that satisfy any of the following criteria:

- If at any time, 1 or more subjects has experienced a Grade 4 or 5 adverse event at least possibly related to study drug.
- The study will be permanently stopped for any Grade 5 adverse event at least possibly related to study drug.

### **13.8 Evaluation of Response**

The determination of response is described in the Section 13.4. All eligible participants having initiated study intervention and having both the pre- and post-intervention biopsies will be considered evaluable for the primary endpoint.

### **13.9 Interim Analysis**

There is no plan for interim analysis. We will randomize 24 subjects total (12 per arm).

### **13.10 Ancillary Studies**

Not applicable

## **14. ETHICAL AND REGULATORY CONSIDERATIONS**

### **14.1 Form FDA 1572**

Prior to initiating this study, the Protocol Lead Investigator at the Lead or Participating Organization will provide a signed Form FDA 1572 stating that the study will be conducted in compliance with regulations for clinical investigations and listing the investigators, at each site that will participate in the protocol. All personnel directly involved in the performance of procedures required by the protocol and the collection of data should be listed on Form FDA 1572.

## **14.2 Other Required Documents**

14.2.1 Current (within two years) CV or biosketch for all study personnel listed on the Form FDA 1572 and Delegation of Tasks form for the Lead Organization and the Participating Organization.

14.2.2 Current medical licenses (where applicable) for all study personnel listed on Form FDA 1572 and Delegation of Tasks form for the Lead Organization and the Participating Organization.

14.2.3 Lab certification (*e.g.*, CLIA, CAP) and lab normal ranges for all labs listed on Form FDA 1572 for the Lead Organization and the Participating Organization.

14.2.4 Documentation of training in “Good Clinical Practice Training” for all study personnel listed on the FDA Form 1572 and documentation of “Protection of Human Subjects” training for all study personnel listed on the Delegation of Tasks form for the Lead Organization and the Participating Organization.

14.2.5 Documentation of Federalwide Assurance (FWA) number for the Lead Organization and all Participating Organizations.

14.2.6 Signed Investigator’s Brochure/Package Insert acknowledgement form

14.2.7 Delegation of Tasks form for the Lead Organization and all Participating Organizations signed by the Principal Investigator for each site and initialed by all study personnel listed on the form

14.2.8 Signed and dated NCI, DCP Financial Disclosure Form for all study personnel listed on Form FDA 1572 for the Lead Organization and all Participating Organizations

## **14.3 Central Institutional Review Board (CIRB) Approval**

Prior to initiating the study and receiving agent, the Investigators at the Lead Organization and the Participating Organization(s) must obtain written approval to conduct the study from the appropriate CIRB. Should changes to the study become necessary, protocol amendments will be submitted to the DCP PIO according to DCP Amendment Guidelines. The DCP-approved amended protocol must be approved by the CIRB prior to implementation

## **14.4 Informed Consent**

All potential study participants will be given a copy of the CIRB-approved Informed Consent to review. The investigator will explain all aspects of the study in lay language and answer all questions regarding the study. If the participant decides to participate in the study, he/she will be asked to sign and date the Informed Consent document. The study agent(s) will not be released to a participant who has not signed the Informed Consent document. Subjects who refuse to participate or who withdraw from the study will be treated without prejudice.

Participants must be provided the option to allow the use of blood samples, other body fluids, and tissues obtained during testing, operative procedures, or other standard medical practices for further

research purposes. If applicable, statement of this option may be included within the informed consent document or may be provided as an addendum to the consent.

Prior to study initiation, the informed consent document must be reviewed and approved by NCI, DCP, the Consortium Lead Organization, and the CIRB. Any subsequent changes to the informed consent must be approved by NCI, DCP, the CIRB, and then submitted to each organization's appropriate internal approval entities for approval prior to initiation.

#### **14.5 Submission of Regulatory Documents**

All regulatory documents are collected by the Consortia Lead Organization and reviewed for completeness and accuracy. Once the Consortia Lead Organization has received complete and accurate documents from a participating organization, the Consortium Lead Organization will forward the regulatory documents to DCP's Regulatory Contractor:

Paper Document/CD-ROM Submissions:

Regulatory Affairs Department  
CCS Associates, Inc.  
[name]  
[name]  
[contact]  
[contact]

E-mail Submissions: [[contact]](mailto:[contact])

Regulatory documents that do not require an original signature may be sent electronically to the Consortium Lead Organization for review, which will then be electronically forwarded to DCP's Regulatory Contractor.

#### **14.6 Other**

This trial will be conducted in compliance with the protocol, Good Clinical Practice (GCP), and the applicable regulatory requirements.

#### **14.7 Anticipated Results and Future Directions**

Oral GCC ligand replacement therapy holds great promise for prevention of colorectal cancer. These agents have favorable pharmacological characteristics, targeting a receptor primarily expressed by intestinal epithelial cells, and active in the intestinal lumen, without appreciable bioavailability and systemic exposure. The pharmacological effects of these agents following chronic exposure endure, without desensitization, in preclinical and clinical studies. Moreover, chronic administration is without obvious untoward effects in mice and humans. Preliminary studies demonstrated that, following oral colonoscopy preparation 0.870 mg of the previous GCC agonist administered for 7 days increased cGMP concentrations in mucosae from the cecum, transverse colon, and rectum. These changes in cGMP were associated with increased phosphorylation of VASP quantified by immunoblot analysis and a reduction in epithelial cell proliferation quantified by Ki67 immunohistochemistry. However, the previous GCC

agonist was without effect on cGMP levels in the rectum in the absence of oral colonoscopy preparation.

The study proposed here advances the utility of this class of agent to prevent colorectal cancer by determining whether or not dolcanatide at 27 mg daily produces the requisite PD changes in cGMP signaling in rectal mucosa (full organ coverage). Once it is determined that dolcanatide is safe and produces cGMP responses in rectal mucosa, we anticipate advancing to a multi-center chemoprevention trial exploring the ability of dolcanatide to reduce the formation of adenoma in patients following chronic (one year) oral daily dosing. If this novel approach is effective in preventing colorectal cancer in patients, it is anticipated that patients at high risk for colorectal cancer (e.g., polyp formation, inflammatory bowel disease) could be placed on lifetime oral GCC ligand replacement therapy. This is consistent with the anticipated use of oral GCC ligand therapy in constipation, in which patients with irritable bowel syndrome-constipation type or chronic idiopathic constipation will receive chronic oral GCC ligand therapy to normalize bowel function.

## **15. FINANCING, EXPENSES, AND/OR INSURANCE**

No clinical trial-related expenses will be incurred by the study participants and/or their insurance carriers. This does not include costs of tests and procedures that are a part of the participant's normal clinical care. This also does not include any injuries or illnesses the participant may have related to their participation on the study. In the event of an injury or illness, the study participant and/or their insurance carrier will be responsible for all expenses related to the injury or illness. There may be expenses incurred by the trial participants related to their study participation, i.e. child care, transportation, etc. Participants who comply with study requirements will be paid \$1320 which is compensation for their time and reimbursement for expenses associated with trial participation.

**APPENDIX A**  
**Performance Status Criteria**

**ECOG Performance Status Scale**

Grade	Descriptions
0	Normal activity. Fully active, able to carry on all pre-disease performance without restriction.
1	Symptoms, but ambulatory. Restricted in physically strenuous activity, but ambulatory and able to carry out work of a light or sedentary nature ( e.g. , light housework, office work).
2	In bed <50% of the time. Ambulatory and capable of all self-care, but unable to carry out any work activities. Up and about more than 50% of waking hours.
3	In bed >50% of the time. Capable of only limited self-care, confined to bed or chair more than 50% of waking hours.
4	100% bedridden. Completely disabled. Cannot carry on any self-care. Totally confined to bed or chair.
5	Dead.

